#### 8.4 Duration of study drug administration and treatment compliance

For the FAS and safety analysis set, descriptive statistics of the compliance rate of the study drug (The 95% CIs of the mean shall not be calculated.) should be calculated to provide the number and proportion of subjects with a compliance rate of  $\geq 80\%$  and  $< 80\%$ . Analysis will be performed by patient cohort in the FAS.

For the FAS and the safety analysis set, the descriptive statistics of the study drug dose period should be calculated (The 95% CIs of the mean shall not be calculated.). Analysis will be performed by patient cohort in the FAS.

For the FAS and safety analysis set, the descriptive statistics of the cumulative dosage of the study drug (The 95% CIs of the mean shall not be calculated.) should be calculated.

## 8.5 Efficacy analysis

As a general rule, efficacy analysis will be performed on the FAS. When necessary, descriptive statistics for continuous variables should be calculated and frequency and proportion will be calculated for discrete variables. Unless otherwise specified, a similar analysis should be conducted for each patient cohort. No data from the day after the rescue therapy implementation date should be included in the efficacy analysis.

### 8.5.1 Analysis of primary endpoint

#### (1) Mean Hb values at Weeks 20 and 24 of the treatment period

Descriptive statistics should be calculated for the primary efficacy endpoint of the mean Hb value at Weeks 20 and Week 24 of the treatment period. The average Hb value at each evaluation time was modeled using MMRM based on the following model, and the average Hb value for Weeks 20 and 24 of the treatment period should be obtained, and the least squares mean (LSMean), its standard error, and 2-sided 95% CIs for the mean Hb values should be calculated., No analysis will be performed for each patient cohort.

[MMRM Model]

- Covariate: response variable value of the first day of the treatment period
- Fixed effects: evaluation period,
- Degrees of freedom adjustment: Kenward-Roger method
- Covariance matrix within subject for each subject: unstructured (type = UN; unstructured)

When it was not converged using unstructured as a covariance matrix within subject variance, the setting of the covariance matrix within subject variance will be changed in the following order, and the analysis will be carried out using the covariance matrix within subject variance converged first.

Heterogeneous Toeplitz (TOEPH) → Heterogeneous AR (1) (ARH [1]) → Heterogeneous CS (CSH) → Toeplitz (TOEP) → First-order autoregressive (AR [1]) → Compound symmetry (CS)

- Random effects: subjects

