### 5.2 Study design

Multicenter, uncontrolled open-label study

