## 6. Target sample size and study period

### 6.1 Target sample size

Forty subjects enrolled in treatment period.

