#### Rationale

Assuming a SD of 1.78 for mean Hb, which is one of the efficacy endpoints for the study, a sample size of 40 subjects allows for value estimation with a precision of mean  $\pm$  0.57 g/dL (95% CI). The SD of 1.78 was calculated from the upper limit of the 80% CI in the MT-6548 300 mg group at the end of the primary efficacy evaluation period of 6 weeks in study CI-0021, a dose-finding study in Japanese patients with NDD-CKD-related anaemia. According to JSDT's "Guideline for Renal Anemia in Chronic Kidney Disease 2015," Hb values vary in a range of about 1 g/dL in normal clinical contexts, so a level of precision of mean Hb  $\pm$  0.57 g/dL (95% CI) should allow for a clinically meaningful analysis. A sample size of 40 subjects should also enable analysis of safety.

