#### 13.3.2 Efficacy

(1) Analysis methods for primary endpoint

1) Mean Hb of treatment period Weeks 20 and 24

To determine mean Hb (mean at treatment period Weeks 20 and 24), mean Hb at each timepoint will be modeled using MMRM with the following model, and mean Hb at treatment period Weeks 20 and 24 and their two-sided 95% CI will be calculated.

[MMRM model]

- Fixed effects: Evaluation period, patient cohort (correction or conversion cohort), interactions of evaluation period × patient cohort (correction or conversion cohort)
- Random effects: Subjects

2) Hb at each treatment period timepoint

Descriptive statistics will be calculated for Hb level at each treatment period timepoint,

and analysis performed taking into account changes over time using MMRM.

- 3) Ratios of subjects with mean Hb within the target range (11.0–13.0 g/dL), <11.0 g/dL, and  $\geq$ 13.0 g/dL at each timepoint in treatment period

Numbers and ratios of subjects with mean Hb at each treatment period timepoint within the target range (11.0–13.0 g/dL), <11.0 g/dL, and >13.0 g/dL will be shown.

- 4) Correction cohort only: Days from the first day of the treatment period required to reach target Hb range (11.0–13.0 g/dL)

Descriptive statistics will be calculated for days from the first day of the treatment period required to reach target Hb range (11.0–13.0 g/dL). A Kaplan-Meier plot will be shown for days from the first day of the treatment period required to reach target Hb range (11.0–13.0 g/dL). Statistical summaries will not include subjects with Hb of  $\geq$ 11.0 g/dL on the first day of the treatment period.

- 5) Correction cohort only: Rate of increase of Hb levels

Descriptive statistics will be calculated for rate of Hb increase.

- (2) Analysis methods for other endpoints

Incidence and ratios will be shown for discrete data, while descriptive statistics will be calculated for continuous data.

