## 8. Statistical Method

### 8.1 Basic matters

#### 8.1.1 Level of significance and confidence coefficient

When implementing tests, level of significance should be set at 2-sided 5%. Confidence interval (CI) will be 2-sided with a confidence coefficient of 95%.

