#### **8.5.4 Statistical issues**

##### **8.5.4.1 Adjustment for covariates**

In the analysis of efficacy, in order to consider the effect of the measurement value of the first day of the treatment period on the change of each measurement, the analysis using the MMRM model (with compound symmetry [CS] for a covariance matrix within subject variance) should be conducted using the measurement value of the first day of the treatment period as a covariate in the general analysis including the analysis of the primary endpoint.

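### Adjusting a single-arm absolute mean Hb for Day-1 Hb, with one slope for all visits, misstates the primary 95% CI: too narrow if dependence on Day-1 Hb persists, possibly too wide if it fades

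*SAP*

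**What the plan says.** The design is a "Multicenter, uncontrolled open-label study" (Protocol 5.2). The first primary endpoint is a level, the mean Hb of Weeks 20 and 24, not a change and not a difference between groups.

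Protocol 13.3.2 models it with "Fixed effects: Evaluation period, patient cohort (correction or conversion cohort), interactions of evaluation period" by cohort, and a random subject effect. Day-1 Hb is not in that model.

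SAP 8.5.1(1) lists "Covariate: response variable value of the first day of the treatment period", keeps evaluation period as the only fixed effect and specifies no Day-1-by-period interaction. The LSMean, its SE and a two-sided 95% CI are reported. SAP 8.5.1(2) uses a similar model, with compound symmetry, for Hb at each visit. SAP 8.5.4.1 makes the adjustment general, "using the measurement value of the first day of the treatment period as a covariate in the general analysis", and includes the primary endpoint. Its stated reason concerns the effect of Day-1 values on the change of each measurement.

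Protocol 13.4 asks that reasons for analysis changes be described. SAP section 9 does not list the added covariate, and nor does the text that replaces section 9 in the errata.

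The sample size rests on precision (Protocol 6.1): "a sample size of 40 subjects allows for value estimation with a precision of mean". The half-width given there is 0.57 g/dL, from an assumed SD of 1.78 g/dL.

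**The concern.** In a randomised comparison a baseline covariate removes noise from a contrast. Here there is no contrast. The target, as far as the documents show, is the mean Hb of treated patients of this kind, and differences in baseline between samples are part of the uncertainty about that mean. A model SE that takes the sample's mean Day-1 Hb as fixed leaves that part out.

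The single slope adds a second problem. If Hb at Weeks 2–6 follows Day-1 Hb more closely than Hb at Weeks 20–24 does, a slope fitted to all visits is wrong for the two visits that form the endpoint.

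What is at stake is the printed uncertainty of the first-listed primary endpoint, in a study sized only for precision.

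**Working it through.** **Inputs.** n = 40 and SD 1.78 g/dL (Protocol 6.1); two-sided 95% CI (SAP 8.1.1); model terms from SAP 8.5.1(1). The correlation r of Day-1 Hb with the Week 20/24 average is not in the documents. It is assumed and varied from 0.2 to 0.7. The LSMean is taken at the observed mean Day-1 Hb, which the SAP does not state.

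**1. The plan's own figure.** t(0.975, 39) × 1.78/√40 = 2.023 × 0.2814 = 0.569, which rounds to 0.57. It reproduces, and it uses the marginal SD with no baseline adjustment.

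**2. Point estimate.** With complete data, centring Day-1 Hb at its sample mean makes the LSMean equal to the raw mean. In every complete-data simulation the difference was 0.0000. The true sampling variance of the estimate is therefore σ²/n with or without the covariate, where σ² is the marginal variance of the Week 20/24 average.

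**3. What the model reports.** Let β be the slope of the Week 20/24 average on Day-1 Hb, b the common slope the model fits, and σₓ² the variance of Day-1 Hb. The residual variance behind the reported SE is

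σ² + [(b − β)² − β²]·σₓ².

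- If the slope is the same at all visits, b = β and this becomes σ²(1 − r²). The CI is too narrow by 1 − √(1 − r²).
- If early visits pull the common slope above 2β, the bracket is positive and the CI is too wide.

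**4. Dependence persists (constant slope).** Half-width = t(0.975, 38) × 1.78 × √(1 − r²)/√40. Coverage of the population mean is from 200,000 simulated single-outcome trials per r.

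| assumed r | √(1 − r²) | half-width (g/dL) | narrowing | coverage |
|---|---|---|---|---|
| 0.2 | 0.980 | 0.558 | 2% | 94.5% |
| 0.3 | 0.954 | 0.544 | 5% | 93.9% |
| 0.5 | 0.866 | 0.493 | 13% | 91.2% |
| 0.7 | 0.714 | 0.407 | 29% | 84.4% |

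Without the covariate, coverage was 95% throughout.

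The repeated-measures structure itself (n = 40, nine post-baseline visits, unstructured covariance, common slope, complete data) agrees. Ratios of adjusted to unadjusted SE were 0.94, 0.85 and 0.70 at r = 0.3, 0.5 and 0.7, with coverage of about 93%, 91% and 84%. The narrowing at r = 0.5 is therefore 13% by formula and 15% by simulation.

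**5. Dependence fades.** In the same structure:

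- Late r = 0.27: fitted b = 0.62 against β = 0.25, so b > 2β. With σₓ = 1 and σ = β/r = 0.926, the SE ratio is √(1 + (0.37² − 0.25²)/0.857) = 1.04. The simulated ratio was 1.03.
- Late r = 0.10: b = 0.63 against β = 0.10. With σ = 1.0, the ratio is √(1 + 0.53² − 0.10²) = 1.13. The simulated ratio was also 1.13.

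Coverage was about 97% in both. A further set of strongly fading patterns gave ratios of 1.07–1.17 and coverage of about 96–98%.

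**6. Missing visits.** With an assumed 20% dropout, the adjusted estimate differed from the completers' raw mean by about 0.04 SD on average, or 0.06 SD when dropout depended on Day-1 Hb.

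**Limits.** The runs in the first two items of step 5 and in step 6 used 400 trials per scenario (coverage error about 2–3 points), with t degrees of freedom of completers minus 2 in place of Kenward-Roger. All correlation patterns are assumed.

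**The case against.** A reader might infer that the primary CI is simply too narrow. The documents do not support that as a certainty. Doses are titrated towards 11.0–13.0 g/dL over 24 weeks (Protocol 8.3), which could weaken the link between Day-1 Hb and late Hb. At r of 0.3 or less the narrowing is no more than about 5%, and under strong fading the direction reverses. This stands: the direction is open.

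A reader might also infer that the covariate never moves the estimate. That needs complete data. Post-rescue data are excluded (SAP 7.3), withdrawals are foreseen (Protocol 12.1), and the MMRM uses no imputed values (SAP 7.4). With missing visits Day-1 Hb carries information, and a plain deletion of the covariate would lose it. This also stands, and it shapes the fix.

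In the constant-slope case the adjusted CI does have 95% coverage for the mean conditional on the enrolled Day-1 values. That is true, but the SAP never states that target, and the ±0.57 was not planned on it.

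An unadjusted interval is already planned: 8.5.1(1) asks for descriptive statistics, and 8.1.2 defines these to include a 95% CI of the mean. This limits the harm. It does not remove it, because that summary uses LOCF for missing visits while the MMRM does not, and the MMRM is the method the protocol names for this endpoint.

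Finally, no test, margin or success threshold depends on this CI. That stands too.

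**Conclusion.** The point holds in a limited form. For absolute Hb in one arm, the Day-1 covariate with a common slope gives no gain in precision for the population mean when data are complete, and it gives an SE that does not describe the sampling error of that mean. The size and direction depend on a correlation the documents do not give: about 5% too narrow at r = 0.3 and 13–15% at r = 0.5 if dependence persists, and roughly 3–17% too wide in the fading patterns examined. The printed CI cannot be set directly against the planned ±0.57 g/dL. The only reason the SAP offers is worded for change from Day 1, and the departure from the protocol model is not listed. The consequence is confined to reported precision.

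**What to change.** For LSMeans of absolute Hb in SAP 8.5.1(1) and 8.5.1(2), enter Day-1 Hb as the first response time point in the repeated-measures model with unstructured covariance, and estimate the Week 20/24 average from it. This keeps the baseline information for subjects with missing visits, gives each visit its own relation to Day-1 Hb, and yields the unconditional SE.

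The alternative is to drop the covariate, as in Protocol 13.3.2. That is simpler but loses the baseline information when visits are missing.

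Keep the covariate, if wanted, only in the change-from-baseline models, and say there that the CI is conditional on the enrolled Day-1 values. Amend 8.5.4.1 to match, state which mean the LSMean targets, and list the departure from the protocol model in SAP section 9 with its reason.

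Cost: one model statement and a few lines of SAP text. The printed CI may become somewhat wider. Adding a tenth time point raises the unstructured covariance from 45 parameters (9 × 10/2) to 55 (10 × 11/2), so non-convergence is somewhat more likely. The SAP's existing fallback sequence can be carried over, but the SE would then rest on the structure chosen.

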### 9.2.3 Efficacy endpoints

Blood sampling will be performed at each study center for measurement by the contract laboratory testing facility. All measurement results will be reported to each study center and the study sponsor.

(1) Hb value

Blood sampling and Hb measurement will be performed on the first day of the screening period, screening period Visit 2, the first day of the treatment period, Weeks 2, 4, 6, 8, 10, 12, 16, 20, and 24 of the treatment period, and the day of discontinuation of treatment.

(2) Ratio of subjects who received ESA rescue therapy

If ESA rescue therapy is performed, type of ESA formulation used, administration route, dose interval, and dosage will be recorded in the CRF.

(3) Ratio of subjects who received red blood cell (RBC) transfusion rescue therapy.

If RBC transfusion rescue therapy is performed, type of RBC formulation used and dosage will be recorded in the CRF.

(4) Study drug dosage

Study drug dosage will be recorded in CRFs.

(5) total number of dosage adjustments

Yes/no for MT-6548 dosage adjustments and post-adjustment dosage will be recorded in the CRF.

(6) Quantity of iron administered

Iron dosage will be recorded in CRFs.

(7) Ratio of subjects who received IV iron

Iron administration route will be recorded in CRFs.

(8) Iron-related measures (serum iron, TIBC, TSAT, and serum ferritin)

Blood sampling and measurement will be performed for serum iron, TIBC, TSAT, and serum ferritin on the first day of the screening period, the first day of the treatment period, Weeks 2, 4, 6, 8, 10, 12, 16, 20, and 24 of the treatment period, and the day of discontinuation of treatment.

(9) Hepcidin

Blood sampling and measurement of hepcidin will be performed on the first day of the treatment period, treatment period Weeks 2, 4, 6, 12, and 24, and the day of discontinuation of treatment.

(10) Haematocrit, RBC count

Blood sampling and measurement will be performed for haematocrit and RBC count on the first day of the screening period, the first day of the treatment period, Weeks 2, 4, 6, 8, 10, 12, 16, 20, and 24 of the treatment period, and the day of discontinuation of treatment.

(11) Reticulocytes (counts and fractions)

Blood sampling and measurement will be performed for reticulocytes (counts and fractions) on the first day of the screening period, the first day of the treatment period, Weeks 2, 4, 6, 8, 10, 12, 16, 20, and 24 of the treatment period, and the day of discontinuation of treatment.

(12) EPO

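### The primary MMRM pairs an unstructured covariance with a redundant random subject effect, so the non-convergence rule could drop UN for a reason unrelated to the data (minor correction)

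*SAP*

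**What the plan says.** SAP 8.5.1(1) describes one MMRM for the mean Hb at Weeks 20 and 24. Its model list contains:

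- "Covariate: response variable value of the first day of the treatment period", so the modelled responses are taken to be the post-baseline visits;
- evaluation period as the only fixed effect listed, with Kenward-Roger degrees of freedom;
- "Covariance matrix within subject for each subject: unstructured (type = UN; unstructured";
- as a separate item at the end, "Random effects: subjects".

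The fallback applies "When it was not converged using unstructured as a covariance matrix within subject variance". The order starts with TOEPH, ARH(1) and CSH and ends with "Toeplitz (TOEP) → First-order autoregressive (AR [1]) → Compound symmetry (CS". The choice rule is that "the analysis will be carried out using the covariance matrix within subject variance converged first".

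Protocol 13.3.2 also lists "Random effects: Subjects" but names no residual covariance structure. There the random effect could be the only source of within-subject correlation, which is a valid model. The SAP added UN and kept the random effect.

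Neither document says that the random effect is dropped under UN, that it is shorthand for the repeated-measures subject identifier, or how to class a singular Hessian or a zero variance estimate. The SAP errata do not touch 8.5.1.

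**The concern.** A random subject intercept adds the same constant to every element of the within-subject covariance matrix. UN already gives each element its own parameter, so any part of the subject variance can be moved into UN without changing the likelihood. The data cannot separate the two.

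This matters because failure to converge is the only stated reason for leaving UN. A redundancy built into the model may be reported by the software as a failed fit, and the written rule cannot tell that apart from a true failure of UN on these data. Two analysts who both follow the SAP could then report the primary CI from different covariance structures. A pre-specified fallback order is meant to prevent exactly that.

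**Working it through.** **Inputs.** Post-baseline Hb visits: "Weeks 2, 4, 6, 8, 10, 12, 16, 20, and 24 of the treatment period" (Protocol 9.2.3), so T = 9. Sample size 40 and SD 1.78 g/dL (Protocol 6.1, SAP 2.3). Two-sided 95% intervals (SAP 8.1.1). Structures from SAP 8.5.1(1).

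**The plan's own figure.** t(0.975, 39) × 1.78/√40 = 2.0227 × 0.28144 = 0.569, which agrees with the stated ±0.57 g/dL. The point below does not depend on it.

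**Step 1: algebra.** Let R be the residual matrix, τ² the subject variance and J the 9×9 matrix of ones. The marginal covariance is V = R + τ²J. Under UN, R has 9 × 10/2 = 45 free elements. For any τ² that leaves V − τ²J positive definite, R = V − τ²J gives the same V and so the same likelihood.

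**Step 2: rank.** The rank of the derivative of the distinct elements of V with respect to all covariance parameters, subject variance included, is:

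| Structure + subject effect | Parameters | Rank, unequal visit variances | Rank, equal visit variances |
|---|---|---|---|
| UN | 46 | 45 | 45 |
| TOEPH | 18 | 18 | 17 |
| ARH(1) | 11 | 11 | 11 |
| CSH | 11 | 11 | 10 |
| TOEP | 10 | n/a | 9 |
| AR(1) | 3 | n/a | 3 |
| CS | 3 | n/a | 2 |

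TOEP, AR(1) and CS assume equal variances, so only the last column applies to them. UN, TOEP and CS are redundant always. TOEPH and CSH lose a rank when the visit variances are equal. Only ARH(1) and AR(1) keep full rank in both cases. Without the subject effect, all seven structures have full rank.

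**Step 3: what a fit would show.** In one simulated data set, −2 log REML (up to a constant) was −360.2019 at every τ² tried, from 0 to 99% of its upper limit of 0.343. The SE of the Week 20/24 mean was 0.1089 throughout. Then 60 trials were simulated by maximum likelihood (n = 40, 4 dropouts, assumed SD 0.9 and correlation 0.85 per 4 weeks):

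- UN alone converged in 60 of 60.
- UN plus subject effect, ordinary inverse: singular information matrix in 60 of 60.
- UN plus subject effect, generalised inverse: converged in 60 of 60, to the same V as UN alone (largest difference below 1e-13).

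**Step 4: size if the chain were followed to the end.** Assume SD 1.78 at each visit, complete data, and correlation ρ per 4 weeks decaying with time. The half-width for the Week 20/24 mean is 1.96 × 1.78 × √[(1 + r)/(2 × 40)], where r = ρ for the true covariance and r is the average correlation over all visit pairs for CS.

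| ρ | Average r | Half-width, true | Half-width, CS | Narrower by |
|---|---|---|---|---|
| 0.70 | 0.505 | 0.509 | 0.479 | 5.9% |
| 0.85 | 0.714 | 0.531 | 0.511 | 3.7% |
| 0.95 | 0.895 | 0.545 | 0.537 | 1.4% |

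**The case against.** The strongest reply is that the redundancy does not touch the reported quantity. Only the split between subject variance and UN is unidentified; V, the LS mean, its SE and the CI are not affected. Step 3 confirms this for any fit that completes, so the reply stands in full for software that zeroes the variance or uses a generalised inverse. The SAP names SAS 9.4 but gives no code, so the documents do not settle which case applies.

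A reader might infer more than the documents support:

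- *That non-convergence is the expected result.* It is possible, not shown. A singular Hessian is also not the same thing as non-convergence, and the SAP defines neither.
- *That the Kenward-Roger step breaks down.* This is not shown. V does not change along the redundant direction. In a check under the Step 3 assumptions, UN alone and UN plus subject effect gave the same adjusted SE (0.14061) and df (37.17) under two different generalised inverses.
- *That the chain would stop at TOEPH.* TOEPH plus subject effect loses rank at equal visit variances, so it is not a safe stopping point.

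Three further points stand. The random-effect line may be loose wording for the clustering unit. UN with 45 parameters on about 40 subjects could fail for data reasons, and a fallback would then be legitimate. The study is uncontrolled and sized for CI precision, so a shift of a few per cent in the half-width changes little.

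**Conclusion.** Read literally, the primary model is over-parameterised under UN, TOEP and CS for any data, and nearly so under TOEPH and CSH when visit variances are close. Because non-convergence is the only trigger, the rule can discard the first-choice structure on account of the model's form. Whether it would depends on software handling that the SAP leaves open. If the fit completes, nothing changes. If it does not, the illustrated effect of ending at CS is a half-width about 1 to 6% narrower, given complete data, a common SD of 1.78 and the assumed decaying correlations; the true effect needs the trial data. A reader might take this as a flaw that invalidates the primary CI, but the evidence does not support that. It is a minor correction that makes the primary model estimable and reproducible as written.

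**What to change.** 1. In SAP 8.5.1(1), delete the random-effect line, or state that it only names the subject identifier of the repeated effect. Model the covariance through the repeated structure alone: UN first, then the listed fallbacks.
2. State that a singular Hessian or a zero variance caused by a redundant term does not count as non-convergence of UN.
3. Apply the same wording to any CS models that reuse this one. SAP 8.5.1(2) calls its model similar to the primary; the later CS models do not restate a random effect, so whether they inherit it should be made explicit.
4. Record the departure from the model in Protocol 13.3.2, with the reason, in SAP section 9, as Protocol 13.4 requires for changes before data lock.
5. In the same edit, reconcile SAP 8.5.4.1 (adjustment for covariates), which can be read as assigning CS to the primary analysis too.

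The cost is a few lines of text and one program statement. Nothing is lost under UN, TOEP or CS (for CS, provided the within-subject covariance is allowed to absorb the subject variance). Under AR(1) and ARH(1) the subject effect is an identifiable component, so deleting it changes those two fallback models. If it is wanted there, keep it for those two only and say so.
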